10.3.2 Efficacy Endpoints

Frequency of bowel movements:

The frequency of bowel movements will be determined via a daily diary where the passage of a bowel movement or absence thereof will be recorded daily throughout the study. *Bowel movements that are the consequence of a rescue medication or suppository will not be counted if they occur within 24 hours of the rescue medication or suppository.* Episodes of incontinence will also be recorded.

Success will be defined as an average complete spontaneous stool frequency increase by 1/week or more compared to baseline or 3 or more complete spontaneous stools/week. Baseline will be the run-in period weekly average and treatment period will be determined as the weekly average during the fixed dose (40 patients) treatment period.

Colonic Motility:

Colonic motility will be determined using the Sitzmarks technique at the beginning of the run-in period and again at the end of the randomized treatment period during Stage 2. The primary measure of interest is the mean colonic transit (MCT) time estimated with a single film (Metcalf et al., 1987).

10.4 Analysis Plan

10.5 Stage 2

Primary analysis: The AE information for the Stage 2 portion of the trial will be summarized as frequency and relative frequency by each dose level and for the LSTDEi for each person.

The primary efficacy outcome variable is whether or not a patient is a "success" or "failure". This is an endpoint based on patient diary entries for the week prior to the endpoint assessment defined as average complete stool frequency increase by 1 or more over baseline, OR 3 or more complete spontaneous stools/week. The patient is deemed a "success" if s/he meets one or more of the criteria listed above, otherwise the patient will be deemed a "failure". The primary analysis will be based on all patients with a baseline assessment (the end of the run-in period, Period 3.1) and an assessment at the end of the fixed-dose period (Period 3.2) and will be a comparison of the proportion of successes with 0.10 (the null hypothesis corresponding to no treatment effect). The proportion of patients for whom the drug was a success at the end of period 3.2 will be estimated with a binomial point estimate and corresponding 95% confidence interval. The observed proportion of successes will be compared to 0.10 using an exact binomial test. ENT-01 will be deemed as demonstrating sufficient efficacy if the two-sided p-value is less than 0.05 for this comparison.

Secondary analyses:

A secondary analysis will compare the proportions of patients who are deemed a success at the end of the randomized period (Period 4) as compared to baseline (end of the run-in period, Period 3.1) between those randomized to the ENT-01 arm and those randomized to the placebo arm. Patients to be included in this analysis will be those who have a baseline assessment (end of the run-in period) and an assessment at the end of the randomization period of the trial, which could be between 34 and 40 patients (17 to 20 in each arm). A Fisher's exact test will be used to compare the proportions of patients who are deemed a success at the end of randomization period (period 4) between the two randomized arms. Another secondary analysis will compare the proportions of patients who are a success (compared to baseline) between the end of the first week of the washout period (period 5) to the end of the randomization period (period 4), for those

patients who were randomized to receive ENT-01 (between 17 and 20 patients). This analysis will consist only of those patients with assessments at baseline (end of run-in period, Period 3.1), the end of Period 4, and the end of Period 5. This analysis will have between 17 and 20 patients and will be done using an exact sign test of equality of paired proportions.

Exploratory analyses:

The first exploratory analysis will of the colonic motility values as measured by an estimate of the mean MCT times. Comparisons will be made within each patient at different time points (i.e. baseline and the end of fixed period) as well as between patient groups (i.e. values observed at the end of randomization period, period 4 for the placebo and the ENT-01 treated groups). The primary endpoint for this analysis is the MCT based on a single film estimate. From a previous study (Ashraf et al., 1997), and estimate for the average MCT for constipated patients with Parkinson's disease is 53.4 hours and an estimate of the standard deviation is 15.9 hours. A paired t-test will be used to compare the mean change in MCT at the end of the fixed period from baseline. A sample size of 34 (40) patients will have 80% power to detect a mean change of 11.1 hours (10.2 hours) with a 0.05 two-sided level of significance and using a paired t-test. This calculation assumed a conservative estimate of 22.4 hours for the standard deviation of the change in MCT, which is the square root of 2 times the variance of the baseline standard deviation. The comparison of the average MCT between the control group and the group randomized to ENT-01 at the end of the randomization period will be made with a two-group t-test.

Exploratory analyses will also be done with respect to the sleep data, the body temperature data, mood, fatigue, hallucinations, overall NMS scale and all other questionnaires and neurocognitive tests. These parameters will be summarized numerically and graphically. There will also be comparisons done of changes over time within a patient (i.e. between baseline, end run-in period, and at the end of the fixed dose period, Period 3.2) and differences between groups (i.e. between patients in the Enterin arm and in the placebo arm at the end of period 4). As before, continuous measurements within a patient will be compared with a paired t-test (transforming the data if necessary) and continuous measurements between patient groups will be compared with a two-group t-test (transforming the data if necessary). In addition, these data will be analyzed using a mixed linear model since there are multiple measurements over time. Categorical data will be

compared with a chi-squared test or a Fisher's exact test if the expected cell counts are too small

for a chi-squared test.

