• The patient will self-administer the Sitzmarks capsule (contains 24 radiopaque markers; Konsyl Pharmaceuticals, Texas, USA) by mouth with water on Days 8,9, and 10 and will consume their usual diet during this period. The patient will abstain from using suppositories or enemas until they return on Day 11. An abdominal XR will be scheduled on Day 11

Day 11 – Site Visit 2

An abdominal XR will be obtained to determine the location and the extent of elimination

of the radiopaque markers. Patients who expel at least 80% (19 or more of the markers) have

grossly normal colonic transit. If remaining markers are scattered about the colon, the condition is

most likely hypomotility or colonic inertia. If remaining markers are accumulated in the rectum or

rectosigmoid, the condition is most likely functional outlet delay. Radiographs will be collected in

electronic format and subsequently analyzed in blinded manner by a centralized reader ([name] MD, and [name], MHA, Division of Gastroenterology and Hepatology, Mayo

Clinic). The patient will be given study medication (B) and a PAC-SYM and PAC-QOL to take

home. This will trigger randomization to treatment or placebo and to PK or no PK.

Day 14- Phone call

Patients will be asked to complete the PAC+SYM and PAC-QOL questionnaires. They

will be instructed to take the medication the following morning on an empty stomach and not to

eat anything for at least 60 minutes thereafter. Baseline complete, spontaneous bowel movements

(CSBM) will be calculated from the diaries at the 14 day phone call as CSBM/entries x

7.Baseline PAC-SYM and PAC-OOL and baseline ease of passage and consistency will also be

obtained at this time-point.

PERIOD 3.2 (Stage 2): Multiple doses

Safety, tolerability and pro-kinetic effect of orally administered multiple-dose ENT-01 in

Sentinel Group followed by Remaining Cohort

Cohort 2 (40 patients, of which 10 comprise the sentinel group):

Duration: 17-19 days

The purpose of this period is to demonstrate the continued pro-kinetic effect beyond that

of a single-dose, to confirm the effective pro-kinetic dose for each individual and to establish the

safety, tolerability and PK of multiple doses of ENT-01. A pro-kinetic dose is defined as the dose

that results in a spontaneous, complete stool on at least two of the three dosing days. Once the

pro-kinetic dose is established, and assuming there are no safety concerns, each patient will be

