CP1001 v0.9, Version Date: 27JUL2017

[figure not shown]
31

kept on that fixed dose for a further 2-4 dosing days (3 days if it falls on a Saturday, 4 days if it falls on a Sunday).

The sentinel group will be a group of 10 patients who did not participate in Stage 1. Patients will be given three consecutive doses of the dose which was found to be safe and tolerable in everybody (STDE) and effective in at least some patients in Stage 1 (75 mg in schematic) at home. Patients will self-administer the study medication *daily* for 3 doses (3 days at each dosing level). The dose will be taken upon awakening on an empty stomach along with 8 oz. of water simultaneously to dopamine). The patient will not be allowed to ingest any food for at least 60 minutes after study medication. The daily diary will be completed and results verbally transmitted and emailed to the study coordinator every evening including on week-end days and entered into the electronic data capture system the same night or first thing in the morning. The coordinator will check in with the patients daily, at the end of the day and determine whether there have been any adverse events or CSBM. If the patient has not produced a CSBM within 24 hours of a dose, on at least two of the three days at a given dose, then the patient will be told to proceed to the higher dose of STDE+25mg (eg. 100mg qd) and also to use a suppository followed by an enema if necessary on the evening of the third day (See rescue diagram below). At the end of the second dosing period (100mg for 3 days), the same criteria will be applied to make a determination as to whether to proceed to STDE+50mg (e.g. 125 mg qd) or not. The incremental dosing will continue up to the consistently clinically effective (pro-kinetic) dose, or to the DLT, whichever comes first. Patients who do not have pro-kinetic effect at DLT will be treated with the highest dose at which they did not have a DLT, if it is at least the STDE dose; if the DLT occurred at the STDE dose, then the patient will be terminated. Should a pro-kinetic response not occur at 175 mg, patients will take 175 mg for the 2-4 additional fixed-dose dosing days and 6 randomized dosing days (assuming randomization is to treatment). DLT will be the dose inducing repeated vomiting or diarrhea within 24 hours of dosing. The lowest dose producing a CSBM on 2/3 consecutive doses will be noted as the pro-kinetic dose (LSTDEi i.e. consistently clinically effective safe and tolerable dose for that particular individual). Patients will be kept on the lowest dose producing a pro-kinetic effect for another 2-4 days prior to randomization in Period 4. The Enterin CMO will review the stool diaries prior to randomization to ensure dosing adequacy. PAC-QOL and PAC-SYM will be repeated prior to randomization at Visit 3. CSBM during the fixed dose period will

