
be calculated as CSBM/#fixed dose days x 7. The primary end-point is obtained by comparing this number to the baseline CSBM obtained at the end of the run-in period.

2: SUPPOSITORY/ENEMA RESCUE USE DURING DOSE ESCALATION IN STAGE

Patients will wear I-Buttons starting with the lowest dose (e.g. 75 mg) and will remove them on day 5 of the wash-out period. The remaining 30 patients will start on STDE (e.g. 75mg) as soon as they have completed the Run-in Period and will follow the same incremental dosing regimen until they reach their LSTDEi or maximum tolerated dose. These regimens and adjustments are shown in the schematic below.

Once the LSTDEi has been established, each patient will remain on that dose for two to four additional days prior to randomization in Period 4 (5 to 7 consecutive days on prokinetic dose)

N.B. Primary end-point is obtained by comparing stool diary at this point with baseline diary on rescue medication at the end of the run-in period.

Visit 3 for non-PK patients (Day before Randomization).

Non- PK patients will come to the site for a visit to return any unused study drug (B), receive 6 daily doses of randomized drug (A or C), Sitzmarks capsules and will complete all the questionnaires listed below. They will be sent home with 6 daily doses of A or C and Sitzmarks capsules and will return for Visit 4 on Day 6 of randomization to complete all the questionnaires.

Go/No-go decisions:

Safety: We are assuming that no more than 1 patients out of forty (2.5%) will have an adverse event of grade 4 or 5 that is at least possibly related to ENT-01 in this Stage. Should there be more than 1 patient with an AE grade 4 or 5 that is at least possibly related to Enterin-0 in this cohort

of 40 patients, the study will be put on an immediate safety hold until an emergency DSMB meeting can be held to evaluate the study for possible discontinuation.

Tolerability: We are assuming that all patients will exhibit a pro-kinetic effect at a dose lower than DLT and less than or equal to 175mg. Patients reaching DLT before a pro-kinetic effect will be terminated if the highest dose for the patient without a DLT was the STDE dose. Otherwise the patient will be treated at the highest dose at which they did not experience a DLT if they are randomized to the treatment arm (or will receive the equivalent dose of placebo).

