Efficacy: We are assuming that a consistent pro-kinetic effect will be observed in all patients. Patients in whom a pro-kinetic effect is not observed at the maximum dose of 175mg will continue to take 175mg for another 2 days and enter the randomized period. If they are randomized to treatment, they will be given 175mg/day for the 6 randomized dosing days.

Individual stopping criteria:

Patients who reach DLT before a pro-kinetic effect, exhibit LFT elevation above 3xULN, have a 10% or greater reduction in body weight or those with a non-DLT gastrointestinal AE > grade 3 within 24 hours of taking ENT-01 that is at least possibly attributable to ENT-01 will be terminated.

Pharmacodynamics: Patient will record bowel movements, ease of passage, consistency and suppository usage in the daily diary throughout the Period and transmit the information to the coordinator every evening.

Sleep assessment: Patients will wear the I-Button throughout the dosing period and remove it only during bathing periods.

STDE DOSE in this example is 75 mg, that being the lowest dose that is safe and tolerable in all subjects and has a prokinetic effect in at least some LSTDEi is the lowest safe and tolerable dose that produces a prokinetic response reached by an individual in at least 2 of 3 days at that dose Subject Day1 Day2 Day3 Day4 Day5 Day6 Day7 Day8 Day9 Day9 Day1 Day12 Day12 Day13 Day14 Day15 Day16 Day17 Day18 Day19 Day20 Day21 Day22 100mg 100mg 100mg 100mg 100mg 100mg 100mg ng 100mg 100mg 100mg 100mg 100mg 100mg 100mg 100mg 125mg 125mg 125mg 125mg 125mg 125m 150mg 150mg 150mg 150mg 150mg 150mg 150mg COHORT 1, 100mg 100mg 100mg 100mg 100mg 100mg Stage 2. SENTINEL PERIOD 3.2, g 125mg ng 150mg 150mg 150mg 150mg 150mg 150mg ROUP N=10 (COHORT 1) 75mg | 75mg | 75mg Safety and tolerability of 3 day dosing. and extension to a total of 5 COHORT 2 doses GROUP, N=32 **RUN-IN PERIOD FOR SUBJECTS 11-40** Day 23 Day24 Day25 Day26 Day27 Day28 Day29 Day30 Day31 Day32 Day 33 Day34 Day35 Day36 Day37 Day38 Day39 Day40 Day41 Day42 Day43 Day44 COHORT 2 GROUP, N=32 11-40

Schematic of Stage 2, Period 3.2 with hypothetical dosing regimen

DSMB: The DSMB will meet at the end of the fixed dose period for the ten sentinel patients.

LSTDEI LSTDEI LSTDEI LSTDEI

PERIOD 4

(Stage 2): Randomized, double-blinded treatment period to determine the effect of orally administered ENT-01 on pharmacodynamics and motility.

Duration: 6 days

Visit 3 for PK patients (Day 1 of randomization):

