The target sample size for Stage 2 is 34 evaluable patients and an additional 6 patients will be accrued to allow for patient drop-outs and terminations; these 40 patients will be different from the 10 patients accrued to Stage 1. A patient is evaluable if s/he has baseline measurements (obtained at the end of the run-in Period, 3.1) and measurements at the end of the fixed dose period (end of Period 3.2). The primary endpoint for Stage 2 is average complete spontaneous stool frequency increase by 1 point over baseline, OR 3 or more complete spontaneous stools per week. A patient will be labeled as a "success" if s/he meets one or more of the criteria above, otherwise the patient will be labeled as a "failure". The primary analysis compares the proportion of patients deemed a success at the end of the fixed-dose period (end of period 3.2) to 0.10, which is the highest proportion of spontaneous resolution of constipation assuming no treatment. A patient is deemed a success or failure by comparing the assessment at the end of the fixed-dose period (Period 3.2) to baseline (obtained at the end of the run-in period, Period 3.1). There could be between 34 and 40 patients with these measurements and each patient will be labeled as a "success" or "failure". It is assumed that without treatment, the success rate would be 10% (null hypothesis). An exact binomial test with a 0.05 two-sided significance level will have 80% power to detect the difference between 0.10 (proportion expected if patients are not treated), p₀, and an ENT-01 proportion, p_E , of 0.29 (0.27) when the sample size is 34 (40). It is assumed that most patients will be deemed a success on the ENT-01 arm and so the study is adequately powered.

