2 STUDY DESIGN OVERVIEW

2.1 Overall Study Design

This is a single-dose, multiple-dose, randomized, double-blinded, placebo-controlled, two-staged study in Parkinson's disease subjects with constipation. The study will consist of two stages, each with run-in period and dosing periods and followed by a wash-out period of 2 weeks. Stage 1 will consist of 10 subjects while Stage 2 will consist of 40 subjects to ensure at least 34 evaluable subjects are obtained. During Stage 1, after providing informed consent, subjects will be screened for eligibility. Qualified subjects will proceed through all the dose escalations of ENT-01 starting at 25 mg and ending at 200 mg or at the dose at which s/he experiences a dose limiting toxicity (DLT). Stage 1 is staggered, where the first two subjects will be administered a single dose of 25 mg first. The rest of the subjects will be dosed after the first two subjects have been observed for 72 hours with no safety concerns. The doses to be tested are 25mg, 50mg, 75mg, 100mg, 125mg, 150mg, 175mg and 200mg. Subjects will then be observed off study drug for two weeks during the wash-out period. STDE (Safe and Tolerable dose in all and pro-kinetic Effect in at least some) dose will be identified and carried over to Stage 2.

In Stage 2 under protocol dated 27 July 2017, subjects who signed the informed consent and are eligible will go through a multiple dose escalation (3 dosing days at each dose) period. The dose range is 75 mg up to 175 mg with an increment of 25 mg for next higher dose. Ten subjects will be in the sentinel group and will be dosed first. The dose at which the subject experiences a consistent pro-kinetic effect (spontaneous, complete stool in at least 2/3 consecutive doses) without a DLT will be the dose selected going forward for that subject. This will be the LSTDEi (i.e. consistently clinically effective safe and tolerable dose for that particular individual). After the LSTDEi is established, subjects will continue to take this dose for 2-4 days, followed by randomization on the LSTDEi dose with a 1:1 ratio to ENT-01 or placebo in block sizes of 4 for a 6-day period (period 4). Seven subjects from the ENT-01 group and three subjects from the control group will be in the PK group and have the PK measurement taken. The rest will be in the non-PK group. All the subjects will then enter the wash-out period for two weeks.

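### The protocol gives two diary windows for the Stage 2 primary endpoint, the SAP settles the choice only by implication, and the 0.10 null is not tied to the 2 to 4 day window being scored

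*Protocol*

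**What the plan says.** **Window.** Three protocol passages define how the Stage 2 primary endpoint is scored.

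- Protocol 3.1, Period 3.2: the CSBM rate during the fixed-dose period is to "be calculated as CSBM/#fixed dose days x 7", and this is compared with the run-in baseline.
- Protocol 10.3.2: the "treatment period will be determined as the weekly average during the fixed dose (40 patients) treatment period".
- Protocol 10.5, primary analysis: "This is an endpoint based on patient diary entries for the week prior to the endpoint assessment".

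The fixed-dose period is short. SAP 2.1 says that once the individual dose is set, "subjects will continue to take this dose for 2-4 days", and Period 3.2 of the protocol gives the same range. The dose is set by a rule on the same outcome: a pro-kinetic dose is one "that results in a spontaneous, complete stool on at least two of the three dosing days".

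**SAP.** Section 1 says the SAP supersedes the protocol's statistical considerations. Section 4.4 uses all diaries of each dosing period, section 4.4.1 divides by diary days and multiplies by 7, and section 7.7.2 tests success at the end of the fixed period. Table 4 (February 2018 amendment) shows a fixed-dose period separate from dose escalation. Section 5.1 declares no changes from the protocol's analyses, and section 9 lists only two dropped secondary analyses.

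**Null.** Success is a rise of at least 1 CSBM per week over baseline, or at least 3 per week. Protocol 10.1.2 tests the success proportion against 0.10, "which is the highest proportion of spontaneous resolution of constipation assuming no treatment". No source or window length is given.

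**The concern.** The two windows can classify the same patient in opposite ways. On the week-prior reading, the days that chose the dose also count towards the outcome, so selection on a good run of days becomes evidence of success. On the fixed-dose reading, a handful of days is scaled up to a week, so one stool can be enough.

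The null matters under either reading. Protocol 10.5 treats a two-sided p-value below 0.05 against 0.10 as sufficient efficacy, and SAP 7.7 removes formal comparisons with placebo. This is then the only formal efficacy test left. If patients whose bowel habit has not changed meet the rule more often than 10% of the time, the test can reject with no drug effect.

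**Working it through.** **1. The plan's own figure.** Inputs from Protocol 10.1.2: exact binomial test, two-sided 0.05, p0 = 0.10. With n = 34 the test rejects at 8 or more successes: P(X ≥ 8) = 0.0169 under 0.10, while 7 or more gives 0.0481, above 0.025. Power at 0.29 is 81.2%. With n = 40 it rejects at 9 or more (tail 0.0155), with power 79.1% at 0.27. The stated 80% reproduces. The arithmetic is sound; the question is what 0.10 refers to.

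**2. What the week-prior window contains.** Three selection days plus 2 to 4 fixed-dose days make 5 to 7 days, so a 7-day look-back reaches all three selection days. This holds for every patient whose dose was set by the two-of-three rule or by reaching the top dose. A patient stepped back after a DLT is different, because days at the DLT level fall in between. Under the two-of-three rule the week already holds at least 2 CSBMs. With baseline b ≤ 1.0, 2 ≥ b + 1, so success is settled before the first fixed-dose day. If no CSBM then occurs on any fixed-dose day, the week-prior window scores a success and the fixed-dose window a failure.

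Qualifying by luck is not rare. At an unchanged rate of 1 per week the daily chance is q = 1/7. Each level qualifies with probability 3q²(1−q) + q³ = 0.055, and over five levels 1 − (1 − 0.055)^5 is about 0.25.

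**3. What the fixed-dose window needs.** The score is 7k/d for k CSBM days in d days.

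- d = 2: one CSBM scores 3.5, a success at any baseline.
- d = 3: one scores 2.33, enough if b ≤ 1.33.
- d = 4: one scores 1.75, enough if b ≤ 0.75. Otherwise two are needed.

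**4. No-effect success rate on the fixed-dose days.** Assumptions: independent days, at most one CSBM per day, daily chance equal to the true weekly rate divided by 7, no rescue, no DLT. Baseline is estimated as X/2, where X is the CSBM count over 14 run-in days, and the patient qualifies if X/2 ≤ 2.

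Example at 1.0 per week with d = 4. Among qualifiers, P(X/2 ≤ 0.5) = 0.1202 + 0.2805 = 0.4007. P(k ≥ 1) = 1 − (6/7)^4 = 0.4602. P(k ≥ 2) = 0.1004. Success = 0.4007 × 0.4602 + 0.5993 × 0.1004 = 0.245.

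The last column is P(Bin(34, p) ≥ 8) over the three window lengths, if every patient had that true rate.

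| True CSBM/week | 2 days | 3 days | 4 days | Test rejects 0.10 |
|---|---|---|---|---|
| 0.25 | 7.0% | 10.2% | 12.4% | 0.2–5.3% |
| 0.5 | 13.8% | 18.6% | 19.6% | 9–35% |
| 1.0 | 26.5% | 27.7% | 24.5% | 62–77% |
| 1.5 | 38.3% | 30.6% | 28.5% | 79–98% |
| 2.0 | 49.0% | 33.0% | 36.2% | 92% to over 99% |

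Without rescue or DLTs the fixed-dose days are independent of the escalation days, so the number of dose levels does not affect this table.

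**5. Sensitivity.** Treat baseline as known and weight 2, 3 and 4 days by 5/7, 1/7 and 1/7 (weekday equally likely). The rate at 1.0 per week is then 5/7 × 0.265 + 1/7 × 0.370 + 1/7 × 0.100 = 0.257. If rescue follows every failed level and the next day cannot count, it falls to 0.162; at 0.5 per week the same change takes it from 0.164 to 0.101. For comparison, the week-prior window with an estimated baseline, five levels and no rescue gives about 23% at 0.5 and roughly 36–37% at 1.0 by simulation.

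**The case against.** The strongest reply is that the SAP governs and has already chosen. It never mentions a week-prior window, it works from dosing-period diaries, it tests at the end of the fixed period, and Table 4 separates escalation from fixed dosing. Much of this stands. A reader might infer that the SAP leaves the choice open, or that the analysis will be run on the week containing the selection days. The documents do not support that. What remains is narrower: under the July 2017 protocol escalation and fixed dosing share Period 3.2, SAP 4.4 speaks only of each dosing period, no start day is stated for Success, and neither section 5.1 nor section 9 records the departure from Protocol 10.5.

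A second reply is that 0.10 may be right. A reader might infer that it is too low whatever the baseline. That is not supported either. Eligible baselines run from 0 to 2 per week with no distribution given. At a true 0.25 the no-effect rate straddles 0.10, and frequent rescue brings 0.5 per week close to it. With exactly 4 days and a baseline of 1.0 known without error, the rate is 0.100; it rises to 0.245 only because baseline is estimated.

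Third, this is a Phase 1/2a trial whose SAP objectives for Stage 2 are safety, tolerability, PK and PD. The plan also reports a confidence interval and continuous CSBM changes, so a reader can apply another benchmark. That softens the consequence. It does not supply the benchmark, and the protocol still attaches an efficacy statement to the test against 0.10.

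Finally, the February 2018 protocol is not supplied. The fixed-dose table does not depend on its dose levels, and the 4-day column matches the fixed-dose period in SAP Table 4.

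**Conclusion.** Two linked defects hold. First, Protocol 10.5 conflicts with Protocol 10.3.2 and the Period 3.2 text on the primary endpoint window. The week-prior version settles success in advance for patients who qualified on the two-of-three rule with baseline 1.0 or less. The SAP points to the fixed-dose days without saying so for Success or listing the change.

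Second, 0.10 is described as spontaneous resolution, not as the chance of meeting this rule on 2 to 4 diary days. Under the assumptions in step 4, that chance passes 0.10 once true baselines rise much above 0.25 per week and is about a quarter at 1.0. Rejecting 0.10 therefore does not by itself show a drug effect. The size depends on the unknown baseline distribution, on day-to-day independence and on rescue use. None of this shows that the drug lacks effect: a success proportion far above these rates would still be informative.

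**What to change.** In SAP 7.7.2, state that Success uses only the fixed-dose diary days after the three qualifying days. Align Protocol 10.5 with this and list the change in SAP section 9.

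Beside the exact test, report a no-drug benchmark from the run-in diaries. For each patient, take all consecutive run-in windows of that patient's own fixed-dose length (13, 12 or 11 windows of 2, 3 or 4 days in 14). Compute the share that meet the success rule against the patient's own baseline, with the same rescue exclusions. Average over patients and give a confidence interval. Do not interpret rejection of 0.10 as efficacy unless the observed proportion is clearly above this benchmark. Patients enter treatment on low run-in counts, so the benchmark is likely a floor, and the report should say so.

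The cost is a few sentences and one derivation from data already collected, with no added patients or visits. The downside to the sponsor is a less favourable reading of a positive test.
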